This randomized, open-label phase II study is designed to compare proportion of patient with major bleedings ever noted during the study. Patients will be assigned to receive prophylactic EACA (experimental arm) or prophylactic platelet (standard of care) in a 1:1 fashion. Previous studies suggest that the proportions of patients with major bleeding will be expected to be 8% and 30% in experimental arm and standard of care arm, respectively. With one sided Fisher's exact test, the sample size of 45 patients in each arm will achieve a power of 80% at the significance level of 5% to test whether prophylactic EACA can prevent major bleeding better than the standard of care. After adjusting for a 10% drop out rate, the actual required sample size will be 50 patients per arm. Therefore, the total sample size of the study will be 100 patients.

Efficacy Analysis

- **Primary Endpoint Analysis** will be performed using a one-sided fisher exact test to compare the proportions of patients with major bleeding during the whole study between the two arms. The significance level is set at 0.05. This primary analysis will be based on the ITT population.
- **Secondary Endpoint Analysis:** one-sided t-test will be used to compare the total number of any bleeding episode noted during the study between the two arms. Two-sided t-test will be employed to compare the total number of units of platelets transfused at the end of the study between the two arms. Appropriate statistical tests (Chi-square test, t-test, Wilcoxon's rank sum test, etc.) will be conducted to compare the each score of the quality of life between the two arms before the study and at the end of the study, respectively. The change of each score of the quality of

life from before the study to the end of the study will also be compared between the two arms. The safety in each arm will be also compared with Fisher's exact test. The analyses of secondary endpoints will be performed on the ITT population and the significance level will be kept at 0.05 for all tests.

Safety Analysis

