The primary objective of this study is to compare the proportion of patients who develop major bleeding episodes (WHO grades 3-4) in the group randomized to receive prophylactic EACA versus standard of care prophylactic platelet transfusions.

2.2 Secondary Objectives:

- To compare the proportion of patients who develop any bleeding episode in the group randomized to receive prophylactic EACA versus standard of care prophylactic platelet transfusions.
- To compare, according to treatment with prophylactic EACA or prophylactic platelet transfusions, the total number of units of platelet transfused
- To compare the quality of life in both arms of the study

2.3 Hypothesis:

This is a non-inferiority trial in which we hypothesize that in thrombocytopenic patients with hematological malignancies, comparable incidence of bleeding will be observed with the prophylactic use of EACA and standard of care arm prophylactic platelet transfusions.

3 Investigational Plan

3.1 Overall Study Design and Plan:

This is a single center, randomized phase 2, open label trial of oral EACA versus platelet transfusions for the prevention of bleeding in thrombocytopenic patients with hematological malignancies.

Eligible patients with acute or chronic thrombocytopenia will be randomized in a 1:1 fashion to receive oral EACA at the dose of 1,000 mg twice daily as a substitute for prophylactic platelet transfusions or standard of care prophylactic platelet transfusions for an untransfused platelet count $< 20 \times 10^9/L$ in the out-patient or in the in-patient setting. Patients will be assessed twice weekly and as needed in between visits for the presence of bleeding. The number of platelets transfused for prophylaxis (arm B) or for therapeutic purposes (both arms) will be monitored. Patients will complete quality of life questionnaire. Adverse events will be assessed and graded according to the National Cancer Institute Common Terminology Criteria for Adverse Events (CTCAE) version 4.0. Bleeding will be assessed and graded according to the World Health Organization (WHO) classification [Appendix 1]. Patients will be assessed according to a protocol-specific schedule of events. Patients will continue treatment on trial until one or more criteria for discontinuation are met. Patients will be supplied with study drug until they discontinue from the study. Patients will be followed for 2 years or death, whichever occurs first.

3.2. Primary Endpoint:

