8.4 Determination of Sample Size

This randomized, open-label phase II study is designed to compare proportion of patient with bleedings noted during the study. Patients will be assigned to receive prophylactic EACA (experimental arm) or prophylactic platelet (standard of care) in a 1:1 fashion. Previous studies suggest that the proportions of patients with major bleeding will be expected to be 8% and 30% in experimental arm and standard of care arm, respectively. With one sided Fisher's exact test, the sample size of 45 patients in each arm will achieve a power of 80% at the significance level of 5% to test whether prophylactic EACA can prevent major bleeding better than the standard of care. After adjusting for a 10% drop out rate, the actual required sample size will be 50 patients per arm. Therefore, the total sample size of the study will be 100 patients.

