8.5.2 Primary Endpoint Analysis

The primary analysis of the primary endpoint will be performed using a one-sided fisher exact test to compare the proportions of patients with major bleeding during the whole study between the two arms. The significance level is set at 0.05. This primary analysis will be based on the ITT population.

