8.5.3 Secondary Endpoint Analysis

One-sided t-test will be used to compare the total number of bleeding episodes noted during the study between the two arms. Two-sided t-test will be employed to compare the total number of units of platelets transfused at the end of the study between the two arms. Appropriate statistical tests (Chi-square test, t-test, Wilcoxon's rank sum test, etc.) will be conducted to compare the each score of the quality of life between the two arms before the study and at the end of the study, respectively. The change of each score of the quality of life from before the study to the end of the study will also be compared between the two arms. The safety in each arm will be also compared with Fisher's exact test. The analyses of secondary endpoints will be performed on the ITT population and the significance level will be kept at 0.05 for all tests.

For the primary and secondary efficacy endpoints, subgroup analyses will be performed by baseline potential prognostic factors. Subgroups will include: age, gender, race, underlying diagnosis, and other disease-related prognostic factors (disease status).

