8.8 Interim Analysis

Three interim analyses are planned after 11 patients in each arm have been randomized and their results have been obtained. Each interim analysis will focus on the primary endpoint, the proportion of patients with major bleeding ever noted during the study. To maintain an overall Type I error rate of 0.05 (1-sided), an O'Brien Fleming approach will be used which requires a 1-sided p-value < 0.001 at the first interim analysis (at 25% of total sample size). If this boundary is not crossed, then the study will continue and the second interim analysis will be conducted at 50% of the total sample size which requires a 1-sided significance level of 0.004. If this boundary is not crossed at the second interim analysis then, the study will continue and a third interim analysis will be conducted at 75% of the total sample size which requires a 1-sided significance level of 0.019. If this boundary is not crossed, the final primary analysis will be performed after completing 100% of the sample size using a 0.043 one-sided significance level.

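### Section 2.3 declares a non-inferiority trial, but the trial is sized and tested for superiority with no margin, so nothing short of superiority can support a claim of comparable bleeding

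*Protocol*

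**What the plan says.** The only sentence under the heading of section 2.3 (Hypothesis) reads, in its main part: "This is a non-inferiority trial in which we hypothesize that in thrombocytopenic patients with hematological malignancies, comparable incidence of bleeding will be observed". It names no bleeding grade and no margin.

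The rest of the protocol describes a different trial:

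- **Synopsis (Sample Size) and section 8.4.** The proportions with major bleeding "will be expected to be 8% and 30% in experimental arm and standard of care arm, respectively". The 45 patients per arm are chosen "to test whether prophylactic EACA can prevent major bleeding better than the standard of care", with a one-sided Fisher test, 5% significance and 80% power; 10% dropout takes this to 50 per arm.
- **Section 8.5.2.** The primary analysis is a "one-sided fisher exact test to compare the proportions of patients with major bleeding during the whole study between the two arms", in the intention-to-treat population.
- **Section 8.8.** O'Brien-Fleming-type levels of 0.001, 0.004 and 0.019 apply at three interim looks, and "the final primary analysis will be performed after completing 100% of the sample size using a 0.043 one-sided significance level".
- **Section 8.5.3.** "One-sided t-test will be used to compare the total number of bleeding episodes noted during the study between the two arms". This is the only between-arm bleeding test among the secondary analyses, and it has no margin either.

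Section 3.1 describes EACA as given "as a substitute for prophylactic platelet transfusions".

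**The concern.** A non-inferiority trial and a superiority trial test different null hypotheses. The first asks whether an excess of bleeding larger than a stated margin can be ruled out. The second asks whether a zero difference can be rejected in favour of EACA. The protocol names the first and builds the second.

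A significant superiority result would also exclude inferiority, so that outcome causes no difficulty. The gap is every other outcome. If section 2.3 is right and the rates are about equal, the planned test will nearly always be non-significant. Read through section 2.3, that result invites a report of comparable bleeding. But the one-sided test gives the same answer when EACA is worse.

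Because EACA replaces prophylactic platelets in this trial, comparability is the conclusion readers will look for. A mistaken claim would support withholding platelets with no evidence limiting the excess of WHO grade 3-4 bleeding.

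**Working it through.** **Inputs.** Sections 8.4, 8.5.2 and 8.8 give rates of 8% (EACA) and 30% (platelets), 45 per arm before and 50 after dropout, a one-sided Fisher exact test at 5%, and look-wise levels of 0.001, 0.004, 0.019 and 0.043. The protocol gives no margin and no common rate under equality. Common rates of 8%, 20% and 30%, the case of 16% versus 8%, and the 10-point margin are therefore assumptions.

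**Step 1: reproduce the stated sample size.** For each pair of event counts (x on EACA, y on platelets), the one-sided Fisher p-value is the hypergeometric probability of x or fewer EACA events given x + y events in total. Power is the sum of the binomial probabilities of all pairs with p ≤ 0.05.

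- 44 per arm, 8% vs 30%: 78.97%
- 45 per arm, 8% vs 30%: 80.05%
- Dropout: 45 / (1 − 0.10) = 50 per arm

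The figures in section 8.4 are thus correct for a test of zero difference. No margin enters them.

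**Step 2: how often the planned test succeeds.** The same enumeration at 50 per arm, and an exact recursion over all four looks at 12, 25, 37 and 50 per arm, give:

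| True rates, EACA / platelets | Final level 0.043 only | All four looks |
|---|---|---|
| 8% / 8% | 1.6% | 1.8% |
| 20% / 20% | 2.4% | 2.8% |
| 30% / 30% | 2.7% | 3.1% |
| 16% / 8% (EACA worse) | 0.05% | 0.06% |
| 8% / 30% (as planned) | 82.5% | 83.1% |

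The last row assumes that all 50 per arm are evaluable. With 45 evaluable and looks at 11, 22, 33 and 45, four-look power is 78.2%.

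**Step 3: two results that the test cannot separate** (50 per arm, Newcombe 90% intervals for EACA minus platelets).

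- 4/50 vs 4/50: p = 0.64; difference 0, interval −9.7 to +9.7 points
- 8/50 vs 4/50: p = 0.94; difference +8 points, interval −3.0 to +19.1 points

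Both are non-significant. The second is compatible with an excess of up to 19 points, and the protocol has no margin against which to judge it.

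**Step 4: what the planned size could support as non-inferiority.** With equal true rates p, one-sided 5% and 80% power, the smallest margin that n per arm supports is (1.645 + 0.842) × √(2p(1 − p)/n). The number per arm for a 10-point margin is 2p(1 − p) × (2.487/0.10)².

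| Common rate p | Margin at 45 per arm | Margin at 50 per arm | n per arm, 10-point margin |
|---|---|---|---|
| 8% | 14.2 points | 13.5 points | 92 |
| 20% | 21.0 points | 19.9 points | 198 |
| 30% | 24.0 points | 22.8 points | 260 |

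These figures ignore the interim looks and dropout.

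**The case against.** The strongest reply is that the operative sections are coherent. Sizing, primary test and boundaries all serve one superiority design, the arithmetic is right, and superiority would imply non-inferiority. On this view section 2.3 is a stray sentence, and nothing in the protocol says that a non-significant test will be read as comparability. The misreporting is a risk, not a plan. All of that is fair. It is why the Fisher test and the 45 per arm are not criticised here, and why the preferred repair is only wording. But the stray sentence is the trial's stated hypothesis, and the document cannot settle which framework was meant.

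A statistical analysis plan that added a margin would not resolve this, because sections 8.4 and 8.5.2 already fix the null hypothesis, the test and the size.

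Three precisions stand:

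- The word better appears only in the synopsis and section 8.4. In sections 8.5.2 and 8.8, superiority is inferred from a one-sided test of two proportions with no margin.
- The t-test in section 8.5.3 concerns the number of episodes, whereas the secondary endpoint in sections 3.3 and 8.3.2 is the proportion of patients with any bleed. If section 2.3 meant any bleeding, that proportion has no non-inferiority test either.
- Superiority excludes inferiority; it does not show that the two incidences are comparable.

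**Conclusion.** The concern holds and must be fixed. Section 2.3 contradicts the synopsis and sections 8.4, 8.5.2 and 8.8 on the primary hypothesis. The design actually built is superiority, with 80.05% exact power at 45 per arm. If the arms are equal, as section 2.3 expects, the trial succeeds only at its type I error rate: 1.6% to 2.7% at the final level and 1.8% to 3.1% over all looks, for common rates of 8% to 30%. A non-significant result does not distinguish equal bleeding from twice as much.

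The contradiction rests on the protocol text alone. The rejection rates depend on the assumed true rates and on 50 evaluable patients per arm; the margins and sizes in Step 4 also depend on the normal approximation. No choice within the range shown changes the conclusion.

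**What to change.** Before any analysis, state in section 2.3 which framework governs, and bring sections 2.3, 8.4, 8.5.2 and 8.8 into line.

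**Superiority, the route that fits what is already written.**

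- Restate section 2.3 along these lines: *EACA lowers the proportion of patients with WHO grade 3-4 bleeding compared with prophylactic platelet transfusion.* Remove the references to non-inferiority and to comparable incidence.
- Add to section 8.5.2 that the risk difference is reported with a two-sided 90% confidence interval and that a non-significant test is not evidence of comparability. The 90% level pairs with the overall one-sided 0.05. An interval matched to the final level would be 1 − 2 × 0.043 = 91.4%; state which is used.
- Cost: a few lines of text, with no extra patients or data.

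**Non-inferiority, if that is truly intended.**

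- State and justify a margin, replace the Fisher test with a test or confidence bound against that margin, rework the boundaries in section 8.8, and restate power and sample size.
- Cost: substantial. An assumed 10-point margin with equal rates needs about 92, 198 or 260 per arm before dropout (common rates of 8%, 20% or 30%), against 45 planned.

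The choice should not wait for the results, because the data would then select the hypothesis.

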1.4 Rationale for the Conduct of this Study

Given the high incidence of platelet refractoriness, and the prolonged duration of thrombocytopenia in patients with hematological malignancies and marrow failure syndromes, alternatives to platelet transfusions are desperately needed. Our institutional experience with EACA provides a unique expertise to further investigate the role EACA can play in the prevention of bleeding in this patient population. We therefore propose to conduct a prospective, randomized, controlled trial to compare EACA versus standard prophylactic platelet transfusion to prevent bleeding in thrombocytopenic patients with hematological malignancies. The objectives of the trial are to address safety and efficacy of EACA as assessed by major and minor bleeding, cumulative platelet transfusion consumption, quality of life and costs in both arms of the study.

Table 2: Characteristics of 44 thrombocytopenic patients who received epsilon aminocaproic acid for the prevention of bleeding

Age, years median (range)	61 (17-82)
Male/female	29/15
Platelet counts $\times 10^9/L$ when EACA started, median (range)	8 (1 – 19)
Patients with platelet refractoriness n (%)	10 (23%)
Duration of thrombocytopenia in days, median (range)	273 (20-1463)
Diagnosis n (%)	
CML	9 (21)
AML	14 (32)
ALL	1 (2)
MDS	15 (35)
CLL	1 (2)
ITP	1 (2)
Lymphomas	1 (2)
Aplastic anemia	1 (2)
Myelofibrosis	1 (2)
Disease Status of patients at the time EACA started	
Active treatment, n (%)	13 (29)
Relapsed/refractory, n (%)	31 (71)
Duration of EACA therapy, median(range) in days	47 (7-209)
Patients without bleeding on EACA, n (%)	26 (59)
Patients with bleeding episodes while on EACA, n (%)	18 (41)
Patients requiring platelet transfusions for bleeds, n (%)	7 (16%)
Grade and location of the 10 bleeding episodes requiring platelet transfusions:	
Grade 4 – CNS*	1

Grade 3 – rectal	1
Grade 2 – hemorrhoids	1
Grade 2 – hematuria **	2
Grade 2 – epistaxis	1
Grade 2 – oral	3
Grade 2 – vaginal	1
Grade and location of the 19 bleeding episodes not requiring platelet transfusions:	
Grade 1- epistaxis	7
Grade 1 – skin bruises	4
Grade 1 – gingival bleed	2
Grade 1 - vaginal	1
Grade 2 – gingival	2
Grade 2 – vaginal	1
Grade 2 - epistaxis	2
Reason for discontinuing EACA, n (%)	
Death	25 (57)
Increased platelets count	18 (41)
Hematuria	1 (2)

*Traumatic brain injury in a car accident

**One patient had 2 episodes of hematuria

2 Study Objectives and Hypothesis

2.1 Primary Objective:

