The primary endpoint is to compare the proportion of patients who develop major bleeding (WHO grade 3 or 4) in each arm.

3.3. Secondary Endpoints:

[figure not shown]
Secondary endpoints include:

- The proportion of patients who develop any bleed in each arm
- The total number of units of platelets transfused in each arm during the study period
- Quality of life as measured by EQ-5D-5L in each arm prior to start treatment and at the end of the study
- Safety in each arm

3.4. Description of Treatment:

Patients will be stratified by expected duration of thrombocytopenia (acute versus chronic), and randomized to receive oral EACA at the dose of 1,000 mg twice daily or the infusion of 1 U of single donor apheresis of platelet when untransfused platelet counts are $< 20 \times 10^9/L$ in the out-patient or $< 10 \times 10^9/L$ in the in-patient, as measured on at least twice weekly CBCs (standard of care for cytopenic patients). Schema of the trial is listed in Figure 3.

Study Schema.

3.5. Randomization:

Patients will be randomized on a 1:1 ratio within each strata (acute vs. chronic) to EACA (Arm B) or standard prophylactic platelet transfusions (Arm A) using a standard randomization table. The study is unblinded.

4. Patient Selection:

4.1. Inclusion Criteria:

- Age > 18 with a hematological malignancy
- Informed consent
- Thrombocytopenia with untransfused platelet counts < 20 x 10⁹/L in the out-patient or in the in-patient setting and one of the following criteria:
 1. Acute thrombocytopenia in patients with hematological malignancies who are in remission and are receiving myelosuppressive consolidation chemotherapy that is expected to induce marrow aplasia for at least 2 weeks; or
 2. Acute or chronic thrombocytopenia in patients with acute leukemia (myeloblastic or lymphoblastic) receiving induction or re-induction chemotherapy that is expected to induce marrow aplasia for at least 2 weeks; or Expected chronic thrombocytopenia in patients with newly diagnosed marrow failure syndromes, myelodysplastic syndromes, aplastic anemia, chronic myelomonocytic leukemia or myelofibrosis; or
 3. Expected chronic thrombocytopenia in patients with relapsed or refractory hematological malignancies; or

4. Hematopoietic stem cell transplant recipients with chronic thrombocytopenia due to chronic GVHD or other causes.

4.2 Exclusion Criteria:

- Acute promyelocytic leukemia
- Patient receiving anticoagulation
- Patient receiving antiplatelet agents

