5.1 Schedule of Events

Table 3. Screening and study procedures to be done through the end of the study. Evaluation visit samples or activities should occur within 3 days of the scheduled study day

	Screening	Cycle 1					Monthly (until Month 6)	End of treatment
	Day <21	Day 1	Day 8 ±3days	Day 15 ±3days	Day 22 ±3days	Day 1 ±3days		
Informed Consent	X							
History and Demographics	X							
Hematological disorder diagnosis and prior therapy	X							
Urine HCG	X							
Vital Signs, ECOG PS and Physical Examination	X	X	X	X	X	X	X	
Concomitant medications	X	X	X	X	X	X	X	

Randomization	X						
CBC*	X	X	X	X	X	X	X
Fibrinogen	X						
Comprehensive metabolic panel**	X	X	X	X	X	X	X
Patient's questionnaire QOL		X					X
Transfusions records		X	X	X	X	X	X
Diary card***		X	X	X	X	X	X
Bleeding score WHO*	X	X	X	X	X	X	X
AE's		X	X	X	X	X	X
SAE		X	X	X	X	X	X

*First 30 days , i.e.: twice weekly or at the discretion of the treating physician, but at least once a week.(If the decision is twice a week, the non-visit day bleeding score may be assessed in person or by phone). After 30 days CBC and bleeding score will be performed according to the standard of care for cytopenic patients **glucose, serum calcium, blood urea nitrogen, creatinine, sodium, potassium, chloride, serum albumin, serum total proteins, carbon dioxide, alkaline phosphatase, aspartate amino transferase and alanine amino transferase. The screening procedures including blood and urine test obtained as part of the routine care, up to 72 hours prior to consenting, may be used to qualify the subject for eligibility and randomization. *** Diary card to be completed by Arm B - EACA

The following describes the procedures/tests required for this study:

Informed Consent: All patients must take part in the informed consent process prior to any study related activity. During the consent process, the person obtaining consent must inform the patient of all elements of informed consent. Adequate time must be allowed for questions and for the patient to make a voluntary decision. No protocol-specific procedures are to be performed until the patient has signed and dated the IRB approved informed consent form. Each patient's participation in the trial begins with the signing and dating of the informed consent form.

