Bleeding score: Bleeding will be graded according with the WHO bleeding scale (Appendix 1) and recorded in the medical records during each visit. For hospitalized subjects enrolled on this trial, bleeding will be described in the daily follow up note by physician, nurse practitioner or physician assistant and graded by the investigator.

End of Treatment or Early Termination Procedures: The End-of-Treatment (or early termination) Visit should be performed within 2 weeks (14 days) of the patient's last dose of study drug or the patient/investigator decision to end treatment, whichever is later.

Follow-up Procedures: Safety: All AEs ongoing or starting within 30 days after the End-of-Treatment must be recorded on the CRF. After this time, ongoing AEs thought to be at least possibly study-drug related and all ongoing SAEs should be followed at least every 4 weeks until they resolve to baseline (or CTCAE grade ≤ 1), stabilize, or are considered to be chronic or irreversible.

Follow-up Procedures: Survival: Survival data will be collected every 12 weeks \pm 2 weeks starting after the last dose of the assigned study treatment or the investigator/patient decision to discontinue treatment, whichever occurs later and continuing for up to 12 months from the time the last patient is randomized to a treatment group. These data do not need to be obtained during a visit; phone contact is acceptable.

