5.3 Study Duration and End of Treatment

The total estimated duration of the study is up to 3 year, including 14 months to accrue patients with up to 1 year for treatment and follow up for the last patient. Patients will be supplied study drug until they discontinue from the study.

End of treatment is defined when untransfused platelet count recover to $> 30 \times 10^9/L$ on 2 measurements obtained 5 days apart. For patients without platelets recovery, end of treatment will be set at 6 months. At that time patients will be taken off treatment and enter a long-term follow-up period for 2 years.

Subjects that completed treatment due to platelet count recover to $> 30 \times 10^9/L$ on 2 measurements obtained 5 days apart whom developed thrombocytopenia > 30 days of end of study and fulfill the inclusions and exclusion criteria are allowed to be re-enrolled in the study. Subjects without platelet recovery that completed 6 months of treatment are not allowed to be re-enrolled in the study

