5.5 Study Termination

If the investigator, Data Monitoring Committee, or regulatory agencies discover conditions during the study that indicate that the study or site should be terminated, this action may be taken after appropriate

consultation between the investigator, and Data Monitoring Committee. Conditions that may warrant termination of the study include, but are not limited to:

- The discovery of a serious, unexpected, or unacceptable risk to subjects enrolled in the study
- Submission of knowingly false information from the research facility to the regulatory authorities
- Insufficient adherence to protocol requirements

Study termination and follow-up will be performed in compliance with the conditions set forth in the guidelines for GCP, International Conference on Harmonization of Technical Requirements for Registration of Pharmaceuticals for Human Use.

6. Safety and Quality of Life Assessments

6.1.1 Safety Assessments: Safety will be assessed by routine physical and laboratory evaluations. AEs will be recorded and the severity will be graded according to the NCI CTCAE v.4.0.

6.1.1. Adverse Events: Type, incidence, severity (graded in accordance with the NCI CTCAE v.4.0), timing, seriousness and relatedness, outcome, action taken with study drug, and treatment will be assessed and documented by the investigator continuously throughout the study. Baseline malignancy-related signs and symptoms will be recorded as AEs during the study if they worsen in severity or increase in frequency. Procedures for following AEs at the end of treatment and beyond are outlined in Section 5.1.

6.2. Quality of Life Assessments: Patients will be asked to fill the EQ-5D-5L. The EQ-5D-5L questionnaire is a validated, self-administered general questionnaire of health-related quality of life (HR-QoL) issues, developed by EuroQoL Group. The questionnaire asks patients to rate their HR-QoL for 5 dimensions: mobility, self-care, usual activities, pain/discomfort, and anxiety/depression. The instrument contains a descriptive element, with patients being asked to rate each dimension on a 5-level descriptive severity scale; and a visual analog scale, where the same dimensions are rated along a 100-point visual ruler. Patients for whom a validated translation exists in a language in which they are fluent will complete the EQ-5D-5L during study visits as outlined in the Schedule of Events.

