8.7 Quality of Life Analysis

Quality of life and health outcomes measures are being collected using the EQ-5D-5L instruments before the study and at the end of the study. Means and medians of raw scores of these questionnaires will be summarized for each treatment group for each domain and be compared between the two arms with t-test or Wilcoxon ranks sum test.

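### Quality of life is scored only at Day 1 and End of treatment, so the between-arm comparison largely misses the period in which the two strategies differ

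*Protocol*

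**What the plan says.** Section 2.2 lists as a secondary objective: "To compare the quality of life in both arms of the study". Section 3.3 fixes the measurement: "Quality of life as measured by EQ-5D-5L in each arm prior to start treatment and at the end of the study". Section 8.3.2 repeats the two time points, and section 8.7 says the instrument is collected "before the study and at the end of the study".

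In Table 3 (section 5.1) the row "Patient's questionnaire QOL" is marked at Day 1 and at End of treatment. Day 8, Day 15, Day 22 and the monthly visits are blank, although bleeding score, adverse events and transfusion records are marked at all of them. Section 6.2 adds no further assessment: patients "will complete the EQ-5D-5L during study visits as outlined in the Schedule of Events".

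The timing of the second score follows from three other places:
- Section 5.3: "End of treatment is defined when untransfused platelet count recover to" above 30 x 10⁹/L on two counts 5 days apart. Without recovery, treatment ends at 6 months.
- Section 5.1: the End-of-Treatment "Visit should be performed within 2 weeks (14 days) of the" last dose or of the decision to stop, whichever is later.
- Section 5.2.2: the same procedures are to be attempted when a patient leaves early for any reason.

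Section 8.5.3 plans to compare the end scores, and the changes from baseline, between arms in the intention-to-treat population.

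**The concern.** The trial compares taking EACA tablets with attending for prophylactic transfusions. Differences in quality of life that come from infusion visits, worry about bleeding or EACA side effects arise while the patient is thrombocytopenic and on the assigned strategy. The schedule has one score before that period and one at or after its close. For many patients the closing event is itself an outcome (recovery or death), so it determines both whether a second score exists and what it reflects. At stake is whether the quality-of-life objective can be answered. The primary endpoint and the bleeding, transfusion and safety data are not affected.

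**Working it through.** The protocol gives no sample size or power for quality of life, so there is no planned figure to reproduce. The check is of the schedule, followed by an illustration from the protocol's own series.

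**1. Time points.** Table 3 has seven visit columns: Screening, Day 1, Day 8, Day 15, Day 22, Monthly and End of treatment. Two are marked for the EQ-5D-5L. Four lie between them (Day 8, Day 15, Day 22, Monthly), and none of these is marked. This agrees with the text of 3.3, 8.3.2 and 8.7.

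**2. When the second score falls, by how treatment ends.**

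| How treatment ends | Second score | What it reflects |
|---|---|---|
| Platelet recovery | At least 5 days after the first count above 30 x 10⁹/L, and up to about 5 + 14 = 19 days if treatment stops at the second count | Period after the strategies cease to differ |
| No recovery, 6 months | At the stop or up to 14 days later | Still thrombocytopenic, near the assigned strategy |
| Early stop for another reason | Up to 14 days after the stop, if the visit is achieved | Near the assigned strategy |
| Death on treatment | None | Missing |

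In the first row, a count above 30 exceeds both prophylactic triggers in section 3.4 (20 for out-patients, 10 for in-patients), and EACA has been stopped.

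**3. Illustration from Table 2 (44 patients, all on EACA).** Under "Reason for discontinuing EACA, n" the table gives death 25, platelet increase 18 and hematuria 1; 25 + 18 + 1 = 44. Duration of EACA had median 47 days and range 7 to 209.

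- *Lower bound.* A median of 47 days means at least 44/2 = 22 patients had stopped by Day 47. With the 28-day month of section 8.1, 6 months is 6 x 28 = 168 days, so the 6-month limit would not touch them. At most 1 of the 22 stopped for hematuria, so at least 22 - 1 = 21 stopped for death or platelet increase: 21/44 = 48%.
- *Upper bound.* All stops for death or platelet increase: 25 + 18 = 43, and 43/44 = 98%. The longest duration, 209 days, exceeds 168, so at least one patient would have met the 6-month limit. The upper bound is reached only if the hematuria patient was the only one to do so.

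Between 48% and 98% of such a series would therefore have no end score or one taken after recovery.

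**4. Could on-treatment scores be obtained?** At least half of the series took EACA for 47 days or more. That is past Day 15, Day 22 and the first monthly visit (Day 29 with 28-day months). Section 4.1 expects aplasia of at least two weeks in the chemotherapy groups, so some of those patients may have recovered by Day 22, and fewer by Day 15.

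**The case against.** The strongest defence is that the endpoint is a simple before-and-after measure, consistently planned at two time points, for an unpowered secondary endpoint in a phase 2 trial. That limits the priority of the point. It does not answer it, because the stated objective is a comparison of the arms. A statistical analysis plan may set rules for deaths and missing scores, but it cannot recover on-treatment scores that were never collected.

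A reader might also infer more than the documents support:

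- *That quality of life is never scored in thrombocytopenic patients close to their strategy.* Section 5.3 provides a 6-month end of treatment without recovery, and section 5.2.2 a closing visit after early discontinuation. The withdrawal criteria in 5.4 and the rule on continued bruising in 6.3.2 can produce such discontinuers. These patients are scored near their strategy.
- *That Table 2 predicts the trial.* Scaling it would give 25/44 x 50, about 28 patients per arm without an end score, and only 1 in 44 scored while still thrombocytopenic. The series is EACA-only, 71% relapsed or refractory, with median thrombocytopenia of 273 days. No 6-month limit and no withdrawal rules like those of 5.4 are stated for it. The trial also enrols patients in remission on consolidation, patients on induction and newly diagnosed patients. The series says nothing about the platelet arm.
- *That the comparison must show no difference whatever the truth.* This is not shown. Selection by survival or discontinuation can push the result either way, and lasting effects of bleeding or thrombosis could persist to the last score.
- *That different timing in acute and chronic patients biases the comparison.* Randomisation is 1:1 within those strata (section 3.5), so this adds heterogeneity rather than imbalance between arms.

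**Conclusion.** The point holds in a limited form. The protocol schedules no EQ-5D-5L between Day 1 and End of treatment. Recovered patients are scored after the strategies have ceased to differ, and patients who die on treatment have no post-baseline score. Only non-recovered patients at 6 months and early discontinuers are scored near their assigned strategy. The planned comparison therefore largely misses the relevant period and rests on a subset selected after randomisation, with bias of unknown direction.

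The 48% to 98% range describes the Table 2 series only and is not a forecast for either arm. A healthier trial population would move patients from missing through death to scored after recovery, and neither group informs the objective. Only a large share of non-recovered 6-month completers or early discontinuers would weaken the point.

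Sections 3.3, 8.3.2 and 8.7 place the second score at the close of the study, whereas Table 3 places it at End of treatment, and sections 3.1 and 5.3 describe 2 years of follow-up. No on-treatment score after Day 1 results under either reading, but the two should be reconciled. The amendment is worth making because it is cheap and the gap cannot be repaired later.

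**What to change.** - **Table 3:** add the EQ-5D-5L in both arms at visits already scheduled during treatment, for example Day 15 or Day 22 and each monthly visit to Month 6.
- **Sections 3.3, 8.3.2 and 8.7:** name one fixed early on-treatment time point as the main between-arm comparison. Include all randomised patients alive at that time, whether or not they have recovered. Keep the end-of-treatment score as supportive. Day 22 is one option; Day 15 is another, since some acute-stratum patients may have recovered by Day 22.
- **Wording:** use one term for the last assessment in 3.3, 8.3.2, 8.7 and Table 3.

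The cost is a protocol amendment, a few minutes of patient time per questionnaire and some extra data entry. No new visits or samples are needed, and no treatment rule changes. Patients who die before the chosen time point will still have no score, but an early time point should keep that group smaller than the present schedule does.
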